### **NOTES:**

This Amendment does not result in a change to either the CRF or the ICF.

### 3. OVERALL STUDY DESIGN AND PLAN DESCRIPTION

#### 3.1. STUDY DESIGN

*The following paragraph [protocol, page 20] has been changed from:*

Recruitment will be competitive among the study sites, until the planned number of patients is enrolled. Competitive recruitment has been chosen to increase the speed of recruitment and to account for any difference in transplant rate among study sites. Each centre will enroll patients as rapidly as possible, up to a maximum of 40 patients (as per the randomization list).

*To:*

Recruitment will be competitive among the study sites, until the planned number of patients is enrolled. Competitive recruitment has been chosen to increase the speed of recruitment and to account for any difference in transplant rate among study sites. Each centre will enroll patients as rapidly as possible, up to a maximum of 40 patients (as per the randomization list). A maximum of 48 patients is allowed for the site of the Primary Investigator.

**Reason:** The study design has been changed considering current patient enrollment status. Specifically, since the first patient randomized to the trial back in February 2014, recruitment is extending considerably longer than originally expected. To date, 86 patients have received TP-IAT, out of 89 randomized. New sites in addition to those originally involved have joined the trial with Cincinnati and UCSF having been initiated early in 2016. Despite this continuous effort, overall enrollment rate across the 9 participating sites is lower than predicted, mainly due to the very rare condition of the TP-IAT procedure, coupled with a non-homogeneous distribution of this procedure across the US states/sites. In particular, enrollment rate has significantly decrease since the site of the Primary Investigator (UMN) has reached the cap of 40 patients (out of 89 randomized to date) allowed at a single site as per protocol. The high enrollment rate of this site actually reflects the high volume of TP-IAT procedures specific for Minnesota. Therefore, considering the importance of:

- maintaining study continuity;
- achieving a timely completion of the trial in order to avoid “dilution” over time of data obtained and potential bias on data reproducibility;
- distribution of TP-IAT procedures across different US sites;

the study design has been changed to allow enrollment at the site of the Primary Investigator up to a total of 48 patients.

## 9. STATISTICAL ISSUES

### 9.2. RANDOMIZATION

*The following paragraph [protocol, page 42] has been changed from:*

The randomization list will be generated with a computer procedure by the method of random permuted blocks in which treatment (in blocks of 4) will be balanced within centres. A master randomization list will be generated, randomizing an excess of patients (a maximum of 40 for each site) to allow competitive recruitment within each centre.

*To:*

The randomization list will be generated with a computer procedure by the method of random permuted blocks in which treatment (in blocks of 4) will be balanced within centres. A master randomization list will be generated, randomizing an excess of patients (a maximum of 40 for each site – additional 8 patients for the site of the Primary Investigator) to allow competitive recruitment within each centre.

**Reason:** To account for the change in study design (see section 3.1.)

**List of Abbreviations and Definitions of Terms**

AE	Adverse Event
ADR	Adverse Drug Reaction
ALT	Alanine Aminotransferase
ATG	Anti-Thymocyte Globulin
AST	Aspartate Aminotransferase
AUC	Area Under the Curve
AUC 0-t	Area under the plasma concentration-time curve from time zero to time t (time of last quantifiable plasma concentration) of reparixin and metabolites
AUC 0-∞	Area under the plasma concentration-time curve from time zero to infinity of reparixin and metabolites
BP	Blood Pressure
°C	Degrees Celsius
CL	Clearance of reparixin and metabolites
CLcr	Calculated Creatinine Clearance (Cockcroft - Gault formula)
C initial	Plasma concentration of reparixin and metabolites just prior to the end of administration
C max	Maximum Plasma Concentration
CMED	Concomitant Medication
cmH 2 O	Centimeters of Water
CPB	Cardiopulmonary Bypass
CRA	Clinical Research Associate
CRF	Case Report Form
CRP	C-reactive Protein
C ss	Steady State Concentration
CXCL8	CXC ligand 8 [formerly interleukin (IL)-8]
ddPCR	Droplet Digital PCR
DMC	Data Monitoring Committee
g	Grams
GCP	Good Clinical Practice
HbA1c	Glycated hemoglobin
HR	Heart rate
kg	Kilogram
IAT	Islet Auto-Transplantation
ICH	International Conference on Harmonization
IRB	Institutional Review Board
IEQ	Islet Equivalent
IND	Investigation New Drug
INR	International Normalized Ratio
ITT	Intent to Treat
i.v.	Intravenous
LD 50	Lethal Dose 50
mg	Milligram
miR-375	microRNA-375
mL	Millilitre
mmHg	Millimeters of mercury
MMTT	Mixed Meal Tolerance Test
ng	Nanogram
NGSP	National Glycohemoglobin Standardization Program
NSAID	Non Steroidal Anti-Inflammatory Drug
PICD	Patient Informed Consent Document
PMN	Polymorphonuclear leukocyte
p.o.	per os (taken by mouth)
PTT	Partial Thromboplastin Time
SAE	Serious Adverse Event
s.c.	Subcutaneous
t 1/2	Elimination half life
t max	Time of maximum plasma concentration of reparixin and metabolites
TPN	Total Parenteral Nutrition
U-CRA	Unblinded-CRA
ULN	Upper Limit of Normal
V z	Volume of distribution of reparixin
XDP	Fibrin Degradation Products
µg	Microgram
λ z	Terminal phase rate constant reparixin and metabolites

## 1. STUDY SYNOPSIS AND OVERALL DESIGN

### Study title

A phase 2/3, multicenter, randomized, double-blind, placebo-controlled, parallel assignment study to assess the efficacy and safety of reparixin in pancreatic islet auto-transplantation.

**Study Number** REP0112 [US IND # 117390]

**Study period** Projected starting date (first-patient-in): December 2013  
Projected completion of patient accrual (last-patient-in): March 2015  
Projected study end date (last-patient-last-visit): March 2016

### Study design

The study will be a phase 2/3, multicenter, double-blind, parallel assignment study. It will involve 100 adult recipients of an intra-hepatic pancreatic Islet Auto-Transplantation (IAT).

Patients will be randomly (1:1) assigned to receive either reparixin treatment (continuous i.v. infusion for 7 days – treatment group) or placebo (control group). The two groups will be balanced within centres. Recruitment will be competitive among the study sites, until the planned number of patients is enrolled.

### Objectives/endpoints

The objective of this clinical trial is to assess whether reparixin leads to improved transplant outcome as measured by the proportion of insulin-independent patients following IAT. The safety of reparixin in the specific clinical setting will be also evaluated.

#### Efficacy endpoints will be:

- The proportion of insulin-independent patients following IAT [Primary endpoint. time frame: day 365±14 after the transplant].
- Area Under the Curve (AUC) for the serum C-peptide level during the first 4 hours of an MMTT, normalized by the number of Islet Equivalent (IEQ)/kg [Time frame: day 75±14 and 365±14 after the transplant].
- Average daily insulin requirements [time frame: day 75±14 and 365±14 after the transplant].
- Basal (2 basal samples in the range between -20 to 0) to 240 min time course of glucose, C-peptide and insulin derived from the MMTT [time frame: day 75±14 and 365±14 after the transplant].
- β-cell function as assessed by β-score [time frame: day 75±14 and 365±14 after the transplant].
- The proportion of patients with an HbA1c ≤6.5% [time frame: day 365±14 after the transplant].
- Cumulative number of severe hypoglycemic events [time frame: from day 75±14 to day 365±14 after the transplant].
- The proportion of patients with an HbA1c ≤6.5% at day 365±14 AND are free of severe hypoglycemic events from day 75±14 to day 365±14 inclusive [time frame: day 365±14 and from day 75±14 to day 365±14 after the transplant].

#### Safety endpoints will be:

- Incidence and severity of Adverse Events and Serious Adverse Events [time frame: throughout the study up to day 365±14 after the transplant].

- Standard laboratory tests including hematology (hematocrit, hemoglobin, red blood cells, platelets, white blood cells, differential white blood cells count), clinical chemistry (sodium, potassium, serum creatinine, blood urea nitrogen, total bilirubin, alanine aminotransferase (ALT), aspartate aminotransferase (AST) and coagulation (International Normalized Ratio (INR), partial thromboplastin time (PTT)) [time frame: pre-transplant hospital admission and post-transplant hospital discharge].
- Vital signs, i.e. blood pressure (BP) and heart rate (HR) [time frame: pre-transplant hospital admission and post-transplant hospital discharge].
- ALT/AST, INR/PTT, fibrin degradation products (XDPs), C-reactive protein (CRP) [time frame: all daily from day 1 up to day 7 after the transplant; ALT/AST also on day 75±14 after the transplant].
- Weight loss from pre-transplant value [time frame: day 75±14 and 365±14 after the transplant].
- Serum level of albumin and pre-albumin (absolute and change from pre-transplant value) [time frame: day 75±14 and 365±14 after the transplant].
- Severity of steatorrhea [time frame: day 75±14 and 365±14 after the transplant].
- Malnutrition risk (poor prognosis, significant risk, increased risk, normal) according to pre-albumin level [time frame: day 75±14 and 365±14 after the transplant].
- Cumulative number of episodes of documented hypoglycemia (documented symptomatic; asymptomatic) [time frame: from day 75±14 to day 365±14 after the transplant].
- Cumulative number of diabetic ketoacidosis-related events [time frame: from day 75±14 to day 365±14 after the transplant].

Exploratory endpoints will be:

- Time course of inflammatory chemokines/cytokines as assessed by serum level of CXCL8, CCL2 (MCP-1), CCL3, CCL4, CXCL10 (IP-10), CXCL9 (MIG), IL-6, IL-10, INF- $\gamma$ , TNF- $\alpha$ , and IL-1 $\beta$  [time frame: pre-infusion hospital admission (2 basal samples collected 6 to 24 hrs apart; both samples will be obtained before surgery and before Investigational Product administration is started) and 6, 12, 24, 72, 120 and 168hrs after the end of islet infusion].
- Proportion of patients who are randomized but do not receive IAT [time frame: transplant day].
- Time course of serum microRNA-375 (miR-375) [time frame: pre-infusion hospital admission (sample will be obtained before surgery and before Investigational Product administration is started) and 6, 12, 24, 72, 120 and 168hrs after the end of islet infusion].

Pharmacokinetic endpoints will be:

- Plasma levels of reparixin (total and unbound) and relevant metabolites (DF2243Y and ibuprofen) [time frame: post-operative day 1, 3, and 5 (steady state) in all patients; just prior to, and then at 1, 3, 5, 6, 8, and 12 hrs after termination of Investigational Product administration in a subset of at least 20-24 patients].

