## 7.2. FOLLOW-UP PROCEDURES AND ASSESSMENTS

Since hospital discharge, patients will self monitor glucose levels and insulin intake according to standard clinical instructions at the site. Insulin will be administered to target fasting and pre-meal glucose levels in the range 80-125 mg/dL, and 2 hour post-prandial glucoses <180 mg/dL. For patients on continuous enteral or parental feeds, insulin will be titrated to maintain glucose in the range 80-140 mg/dL.

The Investigator will identify if- and the date when- it is appropriate for the patient to stop insulin intake, according to standard of centre practice. Regardless the patient is on or off insulin, he/she will report on a Diary Card (see **Appendix 14.7**) his/her self monitored glucose levels for 14 consecutive days prior to the follow-up visits on day  $75 \pm 14$  and  $365 \pm 14$  after the transplant: glucose levels will be measured at least two times a day: 1) after an overnight fast (or anyway before breakfast if the patient is still on a tube feed and TPN); 2) within 2 hours post-prandial. Also, patients still on insulin will report on the Diary Card their daily insulin intake.

Patients will attend the centre for study assessments on 2 follow-up visits scheduled on day  $75 \pm 14$  and  $365 \pm 14$  after the transplant.

At each **visit**, the following will be evaluated/measured in all patients as per centre practice, unless otherwise specified. Measurements, including the actual date and time of assessment, or the date of sampling, will be recorded in the CRF.

- Patient weight.
- Retrospective self-measured glucose and insulin requirement data in the 2 weeks prior to the visit will be reviewed and average (previous week) insulin requirement at each time point as well as insulin-independence / insulin-dependence status will be assessed.
- Retrospective episodes of severe hypoglycaemia in the interval will be assessed as per centre practice. Events of documented hypoglycemia in the interval will be obtained from review of the patient's home glucometer download from between visits and/or patient glucose logs.
- Retrospective severity of steatorrhea in the 4 weeks prior to the visit will be evaluated.
- A blood sample will be taken prior to the meal administration to measure HbA1c, albumin and pre-albumin. ALT/AST will be also measured on day  $75 \pm 5$ .

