#### **7.6.6 Documented Hypoglycemic Episodes**

The cumulative number of documented symptomatic hypoglycemic episodes and the cumulative number of asymptomatic hypoglycemia episodes occurring from Days 75 to 365 inclusive after IAT will be summarized descriptively by treatment group and in total. The cumulative number of episodes for a patient will be the number of episodes recorded on CRF Page 27.1. Treatment groups will be compared using a two-sided t-test or non-parametric Wilcoxon rank-sum test.

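### Asymptomatic hypoglycaemia is compared as a raw count from unstandardised home testing, so the comparison is biased if testing frequency differs with insulin status

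*Protocol*

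**What the plan says.** The safety endpoints in the protocol synopsis and in Protocol 4.2.3 include "Cumulative number of episodes of documented hypoglycemia (documented symptomatic; asymptomatic". Protocol 4.2.3 defines both kinds of documented episode by a measured glucose of 70 mg/dL or lower; they differ in whether typical symptoms are present. Protocol 7.2 says the events are "obtained from review of the patient's home glucometer download from between visits and/or patient glucose logs", and that after discharge "patients will self monitor glucose levels and insulin intake according to standard clinical instructions at the site". It sets no study-wide number of readings between visits and no rule for choosing between the download and the log.

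The one common schedule after discharge is the diary. Patients report "self monitored glucose levels for 14 consecutive days prior to the follow-up visits", and in that period "glucose levels will be measured at least two times a day", whether or not they take insulin. The counting window is about 365 − 75 = 290 days. Only the 14 diary days before the Day 365 visit are standardised within it.

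SAP 7.6.6 states: "The cumulative number of episodes for a patient will be the number of episodes recorded on CRF Page 27.1". Symptomatic and asymptomatic episodes are tabulated separately (Tables 14.3.9 and 14.3.10), and the arms are compared by a two-sided t-test or a Wilcoxon rank-sum test. No number of readings, days with data, rate or offset enters. Protocol 9.4.3 plans only summary statistics for this count. The between-arm test appears first in the SAP, although SAP 1.2 lists no changes from the protocol.

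**The concern.** An asymptomatic episode has nothing to announce it. The number found is the number of low values among the readings the patient chose to take, so it depends on how often the patient tests as well as on how often glucose is low.

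Testing may plausibly depend on whether the patient still takes insulin, and insulin independence is the primary endpoint. A drug effect on that endpoint could therefore change the chance of detection in one arm. Equal and complete follow-up would not remove this, because it concerns readings per day and not days observed.

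At stake is a safety comparison that cannot separate less hypoglycaemia from less testing. It could show a reduction that is only an artefact, or hide a real increase per reading.

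**Working it through.** **1. The plan's nearest figure.** The documents give no figure for documented hypoglycaemia. The insulin-independence rates used below come from the sample-size section (Protocol 9.1, SAP 3.3), which states 90% power for 23% versus 55% with 44 per arm, or 87-90% allowing for discreteness. The unpooled normal formula gives 90.3%, the pooled formula 88.2%, and exact binomial calculation for the uncorrected chi-square 88.8%. The stated figure is reproduced.

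**2. Share insulin-independent, as a proxy for being off insulin.** The IEQ/kg mix is 34/42/24%, with the planned rates by stratum:
- placebo: 0.34×0.13 + 0.42×0.23 + 0.24×0.55 = 0.273
- reparixin: 0.34×0.40 + 0.42×0.55 + 0.24×0.84 = 0.569

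**3. Expected readings per patient.** Let p be the share off insulin and f the readings a day off insulin. Patients on insulin are assumed to take 4 a day. Protocol 6.5.1 sets that minimum for the early post-transplant period; carrying it to Days 75-365 is an assumption. Off insulin, the 14 diary days have a floor of 2 a day.

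Readings = (1−p)×290×4 + p×[276×f + 14×max(f, 2)]

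For f = 2, reparixin: 0.431×1160 + 0.569×580 = 830; placebo: 0.727×1160 + 0.273×580 = 1002.

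| Readings/day off insulin | Reparixin | Placebo | Ratio |
|---|---|---|---|
| 4 | 1160 | 1160 | 1.00 |
| 3 | 995 | 1081 | 0.92 |
| 2 | 830 | 1002 | 0.83 |
| 1 | 673 | 926 | 0.73 |

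With the same risk per reading in both arms, the ratio of readings is also the ratio of expected asymptomatic counts. At f = 2, a true 20% higher risk per reading on reparixin would be cancelled (1.2 × 0.83 = 1.00). That is one illustrative pair of values, not a prediction.

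**4. False significance favouring reparixin.** Counts were simulated with 50 per arm, equal risk per reading and gamma-Poisson variation between patients, and tested at two-sided 5%, so 2.5% is nominal in this direction. One set (t-test and Wilcoxon; gamma shape 1 or 3; 1% or 3% of readings low; 2,000 trials per setting) gave 5-10%, 12-29% and 24-57% at 3, 2 and 1 readings a day. A second set (Wilcoxon; shape 1, 2 or 4; 1% low; 3,000 trials per setting; no diary floor) gave 13-30% at 2 a day and 29-58% at 1 a day.

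**5. When the bias is absent or reversed.** With equal testing (4 a day on and off insulin) the rate is 2.2-2.8%. With no effect on insulin independence it is 2.2-2.5%, even at 1 reading a day off insulin. If patients off insulin tested more often (5 or 6 a day), the mean count would be higher on reparixin: 26.5 versus 24.7 and 29.8 versus 26.3, at 2% of readings low.

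**6. Symptomatic episodes.** If symptoms prompt the test, the count does not depend on routine testing. Simulated with equal true rates, the raw count falsely favoured reparixin in about 2-4% of trials. Dividing by readings would create a bias against reparixin: equal counts over fewer readings give rate ratios near 1/0.83 = 1.2 at 2 versus 4 a day and 1/0.73 = 1.4 at 1 versus 4. Simulated values were about 1.22 and 1.40-1.50. Limited to asymptomatic episodes, the readings denominator brought the false-positive rate back to about 2.8%.

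**The case against.** A reader might infer that the planned comparison is bound to favour reparixin. The documents do not support that. They nowhere give testing frequency by insulin status, and more insulin independence on reparixin is the hypothesis under test. The bias needs both conditions, and it reverses if patients off insulin test more. This objection stands, so the point is conditional.

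A reader might also take 27% and 57% as the shares off insulin throughout the window. They are planned insulin-independence rates at 12 months. Under Protocol 4.2.1 that status also requires HbA1c, fingerstick and laboratory glucose criteria, and under 9.4.6 deaths and losses to follow-up count as failures. They serve only as a proxy, held constant over 290 days.

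A third tempting reading is that all documented hypoglycaemia is affected and that a readings offset should be used throughout. Step 6 shows why not: symptoms can prompt their own test, and an offset would then introduce the opposite bias.

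Finally, the consequence is limited. This safety endpoint is outside the testing sequence in SAP 7.3. Severe hypoglycaemia, which is in that sequence, can qualify through prompt recovery without a glucose value. All this narrows the point. It leaves an asymptomatic count with no denominator, tested formally by the SAP, from which no reader could tell in which direction, if any, testing differed.

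**Conclusion.** The point holds for asymptomatic episodes, conditionally. Detection depends on a reading, testing is not standardised over about 276 of the 290 days, and SAP 7.6.6 tests raw counts. If patients off insulin test less and reparixin brings more patients off insulin, the expected count ratio is 0.92, 0.83 or 0.73 at 3, 2 or 1 readings a day off insulin against 4 on insulin. False significance favouring reparixin then occurs in about 5-10%, 12-30% or 24-58% of trials.

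These sizes rest on assumed testing frequencies, an assumed risk per reading that is equal on and off insulin, assumed patient heterogeneity, and constant insulin status. They show what the analysis is open to, not what will happen. Documented symptomatic episodes are largely unaffected, and the primary analysis is untouched. The change is a cheap improvement to a safety analysis.

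**What to change.** In SAP 7.6.6, for asymptomatic episodes only:

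- Add a between-arm comparison of readings at or below 70 mg/dL per reading recorded in the 14-day diary before Day 365, with the patient as the unit of analysis (for example, a negative binomial model with log number of readings as offset). The diary has one minimum schedule regardless of insulin use.
- State that the sample diary (Protocol Appendix 14.7) has no symptom field, so this analysis counts all low readings.
- Report the Day 75 diary separately, because it largely precedes the counting window.
- Where meter downloads are available, report the number of readings by arm and a per-reading asymptomatic rate as supportive.
- Treat the raw asymptomatic count as descriptive, as Protocol 9.4.3 already plans.

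Do not apply a readings offset to symptomatic episodes.

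The cost of the diary analysis is SAP wording before database lock and one table; the data are already in Listing 16.2.6.4. The downside is precision: the diary covers about 14 of 290 days, and because its schedule is only a minimum, unequal testing can persist above it, which is why the number of readings is the denominator. A new CRF field for readings over the whole interval would not clearly be cheap. The amendment reports 89 patients already randomised, and older downloads or logs may not have been kept, so that part should depend on availability.

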**Number of patients**

The goal of this study is to reach a total of 100 patients who are randomized and receive IAT after total or completion pancreatectomy.

**Inclusion/exclusion criteria**

Patients aged  $\geq$  18 years given written informed consent who are eligible for an IAT following total (or completion) pancreatectomy will be included in this study.

Recipients of a previous IAT (if completion pancreatectomy) as well as patients undergoing total pancreatectomy due to pancreatic cancer or pancreatic benign diseases (e.g. pancreatic pseudocyst, insulinomas, etc.) will be excluded.

Patients who have inadequate renal reserve (calculated creatinine clearance < 60 mL/min according to the Cockcroft-Gault formula), hepatic dysfunction (increased ALT/AST > 3 x upper limit of normal **or** increased total bilirubin above upper limit of normal at local laboratory, except patients with Gilbert's syndrome), a preoperative International Normalized Ratio (INR) > 1.5 or any known coagulopathy, hypersensitivity to ibuprofen or to more than one non steroidial anti-inflammatory drug or to more than one medication belonging to the class of sulfonamides (e.g. sulfamethazine, sulfamethoxazole, sulfasalazine, nimesulide or celecoxib - hypersensitivity to sulphanilamide antibiotics alone, e.g. sulfamethoxazole, does not qualify for exclusion) will be also excluded.

Also, patients will be excluded from study participation if they have concurrent sepsis (as per positive blood culture(s) and/or fever associated with other signs of systemic sepsis syndrome), have received a treatment with systemic steroids in the 2 weeks prior to enrolment (except for the use for physiological replacement only), or any investigational agent (including any anti-cytokine/chemokine agents) or any immune modulators in the 4 weeks prior to enrolment, if they have pre-existing diabetes or evidence of impaired  $\beta$ -cells function (pre-operative fasting blood glucose >115 mg/dL and/or a HbA1c > 6.5%) or require treatment with any anti-diabetic medication (e.g. insulin, metformin, etc) within the 2 weeks prior to enrollment, if they have past or current history of alcohol abuse, if they have evidence of pre-operative portal hypertension (clinical history **and** abdominal/liver imaging by ultrasound techniques).

Pregnant or breast-feeding women or patients unwilling to use effective contraceptive measures (females and males) will not participate in the study.

